 Dapagliflozin therapy in TAVI patients with prior history of HF and diabetes mellitus, reduced LVEF (LVEF ≤ 40%) or renal dysfunction (eGFR 25-75 ml/min/1.73 m2), is associated with reduced 1-year mortality or worsening of HF.

Secondary hypotheses:

- 1) Dapagliflozin therapy in TAVI patients with prior history of HF and diabetes mellitus, reduced LVEF (LVEF ≤ 40%) or renal dysfunction (eGFR 25-75 ml/min/1.73 m2), is associated with reduced 1-year CV mortality
- 2) Dapagliflozin therapy in TAVI patients with prior history of HF and diabetes mellitus, reduced LVEF (LVEF ≤ 40%) or renal dysfunction (eGFR 25-75 ml/min/1.73 m2), is associated with reduced 1-year incidence of AF.
- 3) Dapagliflozin therapy in TAVI patients with prior history of HF and diabetes mellitus, reduced LVEF (LVEF ≤ 40%) or renal dysfunction (eGFR 25-75 ml/min/1.73 m2), is associated with improvement in functional class.

STUDY DESIGN AND ENDPOINTS

DESCRIPTION OF THE STUDY DESIGN

Dapa-TAVI is a pragmatic, controlled, prospective, randomized, open-label blinded endpoint (PROBE design) clinical trial. Patients being discharged after TAVI who meet all inclusion criteria, and none of the exclusion criteria, will be eligible for the enrollment. Patients will be 1:1 randomized to 1 of these 2 arms:

- **Intervention group:** Sodium-glucose cotransporter-2 (SGLT-2) inhibitor therapy with daily oral dose of dapagliflozin 10 mg.
- **Control group:** no SGLT-2 inhibitor therapy with dapagliflozin.

Apart from dapagliflozin therapy (or control), patients will be treated according to current standards (per managing physician prescription).

STUDY ENDPOINTS

> PRIMARY ENDPOINT

• Incidence rate of the composite of all-cause mortality or worsening HF (including hospitalization for HF or an urgent visit resulting in intravenous therapy for HF).

> SECONDARY ENDPOINTS

- Indicence rate of individual components of primary endpoint.
- Incidence rate of CV death.
- Incidence rate of atrial fibrillation (AF).

> TERTIARY ENDPOINTS

- Improvement in NYHA class.
- Safety endpoints:
 - Symptomatic hypotension. Symptomatic hypotension includes postural dizziness with systolic blood pressure < 100 mmHg, and orthostatic hypotension (defined as a decrease of >20 mmHg in systolic blood

- pressure or >10 mmHg in diastolic blood pressure from a supine to a standing position).

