- 9. Does the patient meet all the inclusion criteria and none of the exclusion criteria? (Yes / No, they can only be randomized if yes is selected).
- 10. Has the patient signed informed consent? (Yes / No, they can only be randomized if yes is selected)

Data will be stored in a secure server located at the Coordinator Center (Hospital Álvaro Cunqueiro, Vigo) and will be kept confidential according to legal regulations for data protection.

FOLLOW-UP STRATEGIES

Follow-up will consist on telephone calls and review of patients' medical records.

Once a local investigator identifies that a patient has been admitted for something potentially relevant to the study, he/she will be responsible for collecting the information (admission report, tests, etc..) and send it blinded to the central site for blinded event adjudication.

Follow ups will be done at 2 timepoints: 3 ± 1 , 12 months.

PATIENT ENGAGEMENT / RETENTION STRATEGIES

After randomization, each patient will receive a card identifying the clinical trial that will contain a brief explanation of the aims of it. In the trial card, the arm in which the patient was included (dapagliflozin yes or no) will be stated, together with a central telephone number and email. The patient will be encouraged to contact (phone call/email) for any question related to the trial (either from the patients or from any physician seeing the patient). Any change related to dapagliflozin therapy (stop or initiate dapagliflozin) will be ideally communicated before implementation so the research team can annotate the reasons for the change. Moreover, any change in clinical status (admissions, symptoms, etc..) related to the study may be reported using this telephone number or email. Patients will be asked to carry the study card always with them to facilitate interaction.

No incentives will be established for participating in the study.

PARTICIPANT WITHDRAWAL

Given that this is an open label study with an approved medication and crossovers are not a criterium for withdrawal from the study (see below), the only reason for patient withdrawal from the study is the willingness of the patient to be excluded from the trial.

CROSSOVERS

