Researchers will be offered with the possibility of completing baseline variables by the coordinating center (University Hospital Álvaro Cunqueiro, Vigo, Spain). For this purpose, a copy of the admission report will be requested. To comply with the protection data law, the admission reports should be sent in a secure system.

When accessing via website, there will an option for "upload admission report". The file containing the report (.pdf or .doc) will be selected and uploaded in the system. Since the variables collected in DapaTAVI are those clinically available, it is expected that most of the information will be contained in the admission report.

When accessing via mobile app, there will a possibility of taking a photograph of the admission report with the mobile camera. To avoid retention of photos of the admission report in the mobile phones, the app will not allow selection of previously done photos, only a direct access to the camera via app.

FOLLOW-UP PROCEDURES

• Specific study follow-up. All patients will be monitored by telephone and through their medical records at 3±1 and 12 months, to know their vital status, development of an end-point event or any adverse effect. Whenever a patient presents a clinical event, the medical history will be requested to the local PI. For the DapaTAVI trial, no specific ECG, echocardiogram, or laboratory monitoring are need, only clinical data.

Local researchers will be offered with the possibility of doing telephone calls from the national coordinating center (Hospital Álvaro Cunqueiro, Vigo, Spain). This will be agreed at the beginning of the study or anytime during the march of the trial (i.e. if a center initially is willing to do telephone follow-ups but later thinks this is not possible, the coordinating center will take over this responsibility anytime).

On phone calls, the following fields will be completed after interacting with the patient/family:

- 1. Vital status (alive/death). If death, cause of death (cardiovascular, non-cardiovascular).
- 2. Any HF hospital readmissions or visit to the emergency department (yes/no).

When the patient died or was admitted to a hospital for any cause which may be related to any of the study endpoints, medical reports will be requested to the local investigator.

- 3. Adherence to randomization arm (yes/no). If no, date (month/year) of crossover, and reason for crossover (free text field).
- 4. Functional health status by the NYHA scale.

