> Assumptions:

- Overall alpha value: 0.05
 - o Haybittle-Peto approach for interim monitoring
 - 1st interim analysis: alpha value of 0.001
 - 2nd interim analysis: alpha value of 0.001
 - Final analysis: alpha value of 0.05
- Power: 0.80.
- Test: log-rank (superiority two-sided)
- Minimal treatment effect: HR 0.70.
- 1-year incidence of primary endpoint (controls): 30%
- Accrual period: 2 years
- Follow-up period: 1 year for all patients.
- Percentage of subjects anticipated to withdraw: 5%
- Number of expected primary endpoints: 260.
- > Sample size: 1,020 participants

ADAPTIVE SAMPLE SIZE: The sample size for this study was based on the anticipated incidence of the composite endpoint. It is anticipated that the 1-year incidence of the primary endpoint will be 30% in the control arm and 21% in the dapagliflozin arm (thus, 25.5% in the overall population). To reduce the chances of having an underpowered study secondary to an event rate lower than predicted, a blinded examination of the study overall event rate will be done 3 months before closing the recruitment. At that moment, it is anticipated that >400 patients already underwent 12 months follow-up. In the case that the overall event rate is below 25%, the DSMB will discuss the possibility to doing a re-calculation of sample size according to actual event rate, and the chair will decide if it is needed to increase sample size (thus

extend recruitment period). As this analysis will be performed in a blinded fashion, adjustment for multiplicity is not required and will not be applied.

INTERIM ANALYSIS

Two interim analyses will be performed on primary endpoint and secondary safety endpoints when 33% (86) and 66% (172) of events have been adjudicated. Efficacy and safety interim analyses will be performed following the same methodological guidelines described in this document for the final analysis. Stopping rules for efficacy analysis will be based on the statistical Haybittle-Peto approach, with an overall alpha value 0.05. Safety analyses will be addressed by applying descriptive statistical methods to the data, supplemented by calculation of confidence intervals. No formal statistical stopping rules for safety data will be predefined.

REDUCING BIAS

• Randomization:

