Randomization introduces a deliberate element of chance into the assignment of treatments to subjects in a clinical trial. In this trial, randomization procedure is organized centrally, and it is characterized by being stratified by center and follows a permuted-block design with varying block sizes to reduce predictability of the random sequence.

Blinding:

As this trial follows a PROBE design, open-label and blinded endpoint adjudication are intrinsic characteristics. Masking is no implemented for patient and care provider. Therefore, to reduce potential bias, the endpoint adjudication panel remains blinded to treatment allocation and hard clinical meaningful endpoints have been selected as primary endpoint.

• Multiplicity:

Multiplicity can raise concerns regarding type I error. To address multiplicity problems, two strategies are implemented. First, a composite endpoint is selected as primary endpoint. Second, Haybittle-Peto approach is applied to account for interim analyses.

• External validity:

The pragmatic design of this trial, as evaluated through PRECIS-2 guidelines, increases the generalizability of its conclusions to real daily clinical practice.

DESCRIPTIVE ANALYSIS

The distribution of continuous variables will be analyzed with graphical methods. For normally distributed variables, results will be expressed as mean \pm SD; otherwise they will be represented as median (first quartile to third quartile). Categorical variables will be expressed as absolute frequency (%). Significance testing of baseline differences between treatment groups will be not performed.

PRIMARY ANALYSIS

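### Arm-aware judgement partly decides which possible worsening-HF episodes reach the blinded committee, and the plan has no objective referral rule and no check of referral by arm

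*Combined protocol and SAP*

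**What the plan says.** Under Reducing Bias (Blinding), patients and care providers are not masked, and the stated safeguard is that "to reduce potential bias, the endpoint adjudication panel remains blinded to treatment allocation and hard clinical meaningful endpoints have been selected". The allocation is displayed to the researcher at randomization (Randomization System) and printed on the card the patient carries (Patient Engagement / Retention Strategies).

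Possible events reach the committee by several routes:

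- **Follow-up Strategies.** The step begins "Once a local investigator identifies that a patient has been admitted for something potentially relevant to the study"; that investigator then collects the records and sends them in for adjudication.
- **Follow-up Procedures.** All patients have a call and record review at 3±1 and 12 months. The caller asks, yes or no, about HF readmissions or emergency-department visits. For anyone who has died, or who "was admitted to a hospital for any cause which may be related to any of the study endpoints, medical reports will be requested", and the request goes to the local investigator. The coordinating center may take over the calls, but this is optional.
- **Event Adjudication.** An event may be detected by a local investigator or at a follow-up. The local investigator prepares the anonymised source documents.
- **Patient Engagement / Retention Strategies**, and the section on managing patients after an event. Patients may report study-related changes to a central number or email, and treating physicians are encouraged to contact the coordinating center.

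The plan contains no rule that every unplanned admission or emergency visit is logged or referred, no blinded screening of admissions, no blinding of callers, and no report of referral rates by arm.

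**The concern.** Blinded adjudication can reject an episode that was wrongly referred. It cannot restore one that was never sent. The two filters, potential relevance to the study and possible relation to an endpoint, have no objective criteria and are applied by people who know, or can know, the arm. On the phone, the patient or relative knows the arm too.

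The worsening-HF component is the exposed one. An urgent visit counts if it is unplanned, for decompensation, and leads to intravenous therapy; such episodes are easy to overlook or to attribute to something else. All-cause death is much less exposed, because vital status is asked at each contact. HF is also expected to supply most primary events: the rationale section cites almost one in three patients with prior HF admission readmitted for HF in the first year, against one in ten dying. A difference in referral between arms would therefore pass largely into the primary HR.

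**Working it through.** **Inputs from the plan (Sample Size section, and Description of the Study Design for allocation).** "Overall alpha value: 0.05"; "Test: log-rank (superiority two-sided"); power 0.80; "Minimal treatment effect: HR 0.70"; "1-year incidence of primary endpoint (controls): 30"%; overall incidence 25.5%; withdrawal 5%; "Patients will be 1:1 randomized to 1 of these 2 arms".

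**Plan's own figure.** Schoenfeld events = 4 × (1.960 + 0.842)² / (ln 0.70)² = 247. Then 247 / 0.255 = 969, and 969 / 0.95 = 1,020, which matches the plan. Evaluable patients per arm: 510 × 0.95 = 484.5.

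**Assumptions not in the documents.** Constant hazards; HF share s of first events = 2/3 (range 1/2 to 3/4); a fraction u of HF events unreferred in one arm only, u = 5 to 15%. The calculation treats the final two-sided 0.05 test alone and ignores the interim looks.

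**A. No true effect, loss in the dapagliflozin arm only.** Composite hazard = −ln(0.70) = 0.3567. Apparent HR = 1 − s·u. For s = 2/3 and u = 10%:

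1. HR = 1 − 0.0667 = 0.933.
2. Observed dapagliflozin risk = 1 − exp(−0.3567 × 0.933) = 0.283.
3. Events: control 484.5 × 0.30 = 145.4; dapagliflozin 484.5 × 0.283 = 137.2. About 8 are lost.
4. SE(ln HR) = √(1/145.4 + 1/137.2) = 0.119.
5. Shift = ln(0.933) / 0.119 = −0.58.
6. P(significant in favour of dapagliflozin) = Φ(−1.96 + 0.58) = 0.084, against a nominal 0.025.

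| Unreferred, dapagliflozin arm only | Apparent HR, s = 3/4 to 1/2 | False significant benefit, s = 1/2 to 3/4 |
|---|---|---|
| 5% | 0.963 to 0.975 | 4.0 to 5.1% |
| 10% | 0.925 to 0.95 | 6.3 to 9.6% |
| 15% | 0.888 to 0.925 | 9.6 to 16.6% |

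Splitting the composite by a one-year mortality of 10% or 15%, instead of by an HF share, gives an HR of 0.93 to 0.95 and 7 to 9% at u = 10%.

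**B. Loss in the control arm only, u = 10%.** With no true effect, the apparent HR = 1 / (1 − s·u) = 1.05 to 1.08, against the drug. With a true HR of 0.70, the apparent HR = 0.70 / (1 − s·u) = 0.74 to 0.76, and power is 58 to 67%.

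**C. Equal 10% loss in both arms, true HR 0.70.** The HR stays at 0.70. Events fall from about 252 to between 236 and 242, and power from 81% to 78 to 79%.

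The size of any bias therefore depends on the difference in referral between arms, and its direction on which arm loses more.

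**The case against.** The local investigator is not the only gate. Every patient in both arms has scheduled calls with record review; the phone question covers emergency visits as well as HF readmissions; patients have a central contact line; and physicians are asked to make contact about clinical events whether or not these are listed endpoints. Follow-up Procedures also asks for the medical history whenever a clinical event occurs, which can be read broadly. The narrower filter covers any study endpoint, and atrial fibrillation and genito-urinary infection are endpoints, so some ambiguous admissions would be sent in anyway. An event is lost only if all these routes miss it, and the HR is biased only if they miss unequally. Further, the HF-hospitalization definition requires a primary diagnosis of HF, so many ambiguous admissions would fail adjudication even if referred.

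Most of this stands, and it rules out reading the investigator as sole gatekeeper. It does not close the gap. No caller is required to be blinded, and the same call asks about adherence to the allocated arm. The phone question does not ask about admissions under another label. Contact by patients and physicians is voluntary. Once an episode comes to light, a relevance judgement still governs the request for reports, and the local investigator still supplies them. The primary-diagnosis criterion argues for a tighter trigger than one that sends in every breathless patient; it does not justify having no trigger.

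**Conclusion.** The gap is real and worth closing: detection and referral of worsening-HF events rest partly on unblinded judgement, with no objective rule and no monitoring by arm. The parallel routes reduce the risk without removing it.

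A reader might infer that the primary endpoint is biased, and in favour of dapagliflozin. The documents do not support that. Nothing in them shows that referral would differ by arm or in which direction. Loss in the control arm alone would work against the drug, and equal loss costs only two or three points of power.

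The 6 to 10% false-positive figure is an illustration. It rests on an assumed 10% loss confined to the dapagliflozin arm, an assumed HF share of one-half to three-quarters, and no true effect. It shows that about 6 to 9 unreferred first events in one arm would be enough to matter.

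**What to change.** In Follow-up Strategies and Follow-up Procedures, replace the discretionary filter with a trigger applied identically in both arms. Refer:

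- every death;
- every unplanned visit or admission in which an intravenous diuretic, inotropic or vasoactive drug was given;
- every unplanned admission whose report lists HF or pulmonary congestion among the diagnoses.

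The committee then applies the existing definitions, including the primary-diagnosis criterion. The investigator's opinion on cause may be recorded but should not decide referral. Change the phone question to any hospital admission or emergency visit for any reason. Report admissions, referrals and confirmations by arm to the DSMB and in the final report, so that an imbalance can be seen.

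**Cost.** Protocol wording, one changed phone question, more dossiers for the existing committee (at least two of its members review each event) and a lower confirmation rate. The reports are routine documents and no new tests are needed. The documents give no basis for estimating the extra dossiers.

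**Limit.** The change does not remove open-label influence on the treating physician's primary diagnosis or on the decision to give intravenous therapy.

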	Incidence rate of atrial fibrillation (AF)
	Tertiary endpoints: 1) Change in functional class (NYHA). 2) Safety
	endpoints (incidence rate of Major hypoglycemia, Symptomatic hypotension,
	Genito-urinary infections, Ketoacidosis, Amputation, and Necrotizing Fasciitis
	of the Perineum (Fournier's Gangrene). 3) Crossovers.
Population	Patients with aortic stenosis and prior history of HF or reduced LVEF
	discharged after TAVI.
Inclusion criteria	• ≥18 years old.
	Severe aortic stenosis underwent TAVI.
	Prior heart failure admission and one of the following criteria:
	➤ Left ventricular ejection fraction ≤ 40% or
	Diabetes mellitus or
	➤ Estimated glomerular filtrate rate 25-75 ml/min/1.73 m2
Exclusion criteria	Known allergy or intolerance to SGLT2 inhibitors.
	Concomitant therapy with sulfonylurea or SGLT2 inhibitors.
	• Systolic blood pressure < 100 mmHg or diastolic blood pressure < 50
	mmHg.
	An estimated glomerular filtration rate (GFR) below 25 ml per
	- , , , -

[figure not shown]

	minute per 1.73 m2.
	_
	Chronic cystitis and/or recurrent urinary tract infections (2 or more in
	the last year)
	Poor control of diabetes mellitus that requires SGLT-2 inhibitor
	prescription on discharge according to treating physician judge.
	Any medical condition that, in the investigator's judgment, would
	seriously limit life expectancy (less than one year).
	Pregnant or breast-feeding patients
	Patients participating in other clinical trials.
Phase	IV.
Number of Sites	26.
Study Drug	Dapagliflozin 10-mg daily dose.
Comparator	Control (no dapagliflozin).
Power calculation	- Anticipated effect size: dapagliflozin treatment will be associated with a 30%
	reduction in the incidence rate of the primary composite endpoint
	Anticipated incidence control arm: 30%
	Anticipated incidence in dapagliflozin arm: 21%
	- Power: 0.8
	- Anticipated incidence of withdrawals/losses in follow-up: 5%
	- Sample size (including withdrawals): 1,020 (510 per treatment arm)
Events	Events will be adjudicated by a blinded committee after reviewing information
adjudication	sent by local investigators
Interim analyses	Two interim analyses will be performed on primary endpoint and secondary
	safety endpoints when 33% and 66% of events have been adjudicated (81 and
	172 events respectively).
Chronogram	2021-2024
	Q1 2021: Start of inclusion
	Q1 2022: Half way with inclusion (510 patients)
	Q1 2023: Anticipated end of inclusion (1,020 patients)
	Q1 2024: End of follow-up

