- Major hypoglycemia. Major hypoglycemia is defined as an event where all the following criteria were confirmed by the investigator: (1) the patient experienced symptoms of severe impairment in consciousness or behaviour; (2) the patient needed external assistance; (3) intervention was needed to treat the hypoglycaemia; and (4) there was prompt recovery of acute symptoms following the intervention.
- Ketoacidosis.
- Genital or Urinary Infections
- Amputation
- Necrotizing Fasciitis of the Perineum (Fournier's Gangrene)
- Crossovers (incidence rate and reasons).

[figure not shown]
STUDY ENROLLMENT AND WITHDRAWAL

Estimated date to initiate enrollment is Q1 2021. It is anticipated that enrollment will be performed in a 2 years time frame. Screening of patient candidates will be done during index hospital admission (i.e. admission for TAVI). Individuals meeting inclusion criteria (and not meeting any exclusion criterion) will be invited to participate immediately before hospital discharge. Patients may be recruited after hospital discharge as long as randomization is one within two following weeks after TAVI.

Women and members of minority groups and their subpopulations will be included in accordance with the NIH (National Institutes of Health) Policy on Inclusion of Women and Minorities as Participants In Research Involving Human Subjects.

Anticipated recruitment rate.

Anticipated cumulative recruitment

PARTICIPANT INCLUSION CRITERIA

- Patients (≥18 years, both genders) with severe aortic stenosis (aortic valve area ≤ 1.0 cm2, or indexed aortic valve area ≤ 0.6 cm2/m2, or jet velocity ≥ 4.0 m/s, or mean gradient ≥ 40 mmHg) underwent TAVI.
- ➤ Prior heart failure admission and one of the following criteria:
 - Left ventricular ejection fraction $\leq 40\%$ or
 - o Diabetes mellitus or
 - o Estimated glomerular filtrate rate 25-75 ml/min/1.73 m2

PARTICIPANT EXCLUSION CRITERIA

An individual who meets any of the following criteria will be excluded from participation in this study:

- 1) Known allergy or intolerance to SGLT2 inhibitors.
- 2) Concomitant therapy with sulfonylurea or SGLT2 inhibitors.
- 3) Systolic blood pressure < 100 mmHg or diastolic blood pressure < 50 mmHg.
- 4) An estimated glomerular filtration rate (GFR) below 25 ml per minute per 1.73 m2.
- 5) Chronic cystitis and/or recurrent urinary tract infections (2 or more in the last year)

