- 6. Death due to CV Haemorrhage: refers to death related to haemorrhage such as a non-stroke intracranial haemorrhage, non-procedural or non-traumatic vascular rupture (e.g., aortic aneurysm), or haemorrhage causing cardiac tamponade.
- 7. Death due to Other CV Causes: refers to a CV death not included in the above categories but with a specific, known cause (e.g., pulmonary embolism or peripheral arteria disease).
- **Non-CV Death:** Non-CV death is defined as any death not covered by CV death and falling into one of the following categories:
 - 1. Pulmonary failure
 - 2. Renal
 - 3. Gastrointestinal causes
 - 4. Hepatobiliary
 - 5. Pancreatic
 - 6. Infection (includes sepsis)
 - 7. Inflammatory (e.g., Systemic Inflammatory Response Syndrome / Immune (including autoimmune, may include anaphylaxis from environmental (e.g., food allergies)
 - 8. Haemorrhage that is neither CV bleeding or stroke
 - 9. Non-CV procedure or surgery
 - 10. Trauma
 - 11. Suicide
 - 12. Non-prescription drug reaction or overdose

- 13. Prescription drug reaction or overdose
- 14. Neurological (non-cardiovascular)
- 15. Malignancy
- 16. Other, please specify.
- Undetermined Cause of Death: Undetermined Cause of Death refers to a death not attributable to one of the above categories of CV death or to a non-CV cause. Inability to classify the cause of death may be due to lack of information (e.g., the only available information is "patient died") or when there is insufficient supporting information or detail to assign the cause of death. In general, most deaths should be classifiable as CV or non-CV, and the use of this category of death, therefore, should be discouraged and should apply to few patients in well-run clinical trials.
- Atrial fibrillation (AF): The diagnosis of AF is based on the physical finding of an irregular supraventricular heart rhythm and is confirmed with an ECG or rhythm strip.
- Functional status: Functional status will be measured as New York Heart Association (NYHA) functional classification of heart failure for dyspnea.

EVENT ADJUDICATION

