Primary analyses will be performed in the "full data set" in an intention-to-treat fashion. The intervention arm will be compared against the control arm for the composite primary endpoint. Time-to-event will be evaluated using the Kaplan-Meier survival analysis followed by multivariable Cox proportional hazards model. Hazard ratios (HR) with corresponding 95% confidence intervals will be calculated for treatment effect estimation. All patients without an event will be censored at last day of follow-up. Patients that withdraw from follow-up will be considered censored on the day of withdrawal. Due to the randomization process and the large sample size of the trial, it will be not expected the presence of covariate relevant imbalances between treatment groups. However, for exploratory purpose, standardized differences will be calculated. Those known prognostic factor presenting an imbalance higher than 0.1 standardized difference will be included in the multivariable Cox model. For all tests, we will use 2-sided p-values with alpha ≤0.05 level of significance.

SECONDARY ANALYSIS

The secondary endpoints will be the individual components of the primary composite endpoint, besides CV mortality and the development of new atrial fibrillation. Analyses will be performed following the same guidelines described for primary analysis. Multiplicity adjustment will be not implemented because the hierarchical structure between primary and secondary endponits.

To better explore the treatment effect under ideal circumstances (explanatory approach), primary and secondary endpoint analyses will be replicated in the "per protocol data set" using same methods described above.

SUBGROUP ANALYSIS

All subgroup analyses will be performed using interaction models based on the primary analysis model, also including the subgroup in question and the treatment-subgroup interaction as factors, and presented as treatment hazard ratios for each subgroup and the interaction p-value. Subgroups will be specified in the endpoints section below.

PRE-SPECIFIED SUB-GROUP ANALYSES

- > Diabetic vs non-diabetic patients.
- ightharpoonup LVEF < vs > 40%.
- \geq 80 years vs < 80 years of age on recruitment
- ➤ Males vs females
- ➤ Atrial fibrillation versus sinus rhythm
- > Hypertensive vs normotensive patients
- ➤ Moderate-severe vs mild LVH.
- > Treatment with beta-blockers vs. no beta-blockers

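### The follow-up call form has no question on atrial fibrillation or the six safety endpoints, so their capture rests on unstructured routes that may work differently in the two open-label arms

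*Combined protocol and SAP*

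**What the plan says.** AF is a secondary endpoint. The Secondary Analysis section describes the secondary endpoints as the components of the primary, "besides CV mortality and the development of new atrial fibrillation". Under Definitions, an AF diagnosis "is confirmed with an ECG or rhythm strip". Six safety endpoints are listed among the tertiary endpoints: symptomatic hypotension, major hypoglycaemia, ketoacidosis, "Genital or Urinary Infections", amputation and Fournier's gangrene.

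The process diagram names AF and the safety endpoints as assessments at Visits 2 and 3. The Study Schedule table has rows for endpoint events and adverse events at both times.

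Follow-up Procedures then gives the content of the call: "On phone calls, the following fields will be completed after interacting with the patient/family". The list has four items:

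1. Vital status and cause of death.
2. HF readmission or emergency department visit.
3. Adherence to the allocated arm, with date and free-text reason for any crossover.
4. NYHA class.

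Under item 2, reports are requested "When the patient died or was admitted to a hospital for any cause which may be related to any of the study endpoints". The same section also states: "For the DapaTAVI trial, no specific ECG, echocardiogram, or laboratory monitoring are need, only clinical data".

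**The concern.** The plan says several times that AF and safety events will be found at the two follow-up contacts, but the only itemised set of follow-up questions asks about none of them. Many such events, notably AF, hypotension and genito-urinary infection, can be managed without admission. They then depend on someone noticing them in the records or volunteering them.

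Two things are at stake. First, incomplete capture that is equal in both arms costs precision for AF and makes a true safety difference harder to see. Second, capture that is unequal between arms can create or hide a difference. Reducing Bias states that patients and care providers are not masked. Blinded adjudication does not help here, because the committee sees only events that have already been reported. The DSMB reviews safety endpoints at both interim analyses descriptively, with no formal safety rule, so it would have no ready way to tell a capture artefact from a real excess.

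**Working it through.** **Capture routes, side by side**

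| Route | Section | Covers AF and safety? | Structured and identical by arm? |
|---|---|---|---|
| Call fields 1, 2 and 4 | Follow-up Procedures | No (death, HF or emergency visit, NYHA) | Yes, but for other outcomes |
| Call field 3, crossover reason | Follow-up Procedures | Only if the event led to a treatment change | No |
| Record review at 3±1 and 12 months | Follow-up Procedures, Study Schedule | Yes, in general terms | Records and search items not specified |
| History requested after a clinical event | Follow-up Procedures | Yes, once the event is known | Presupposes detection |
| Report by the local investigator | Follow-up Procedures (general monitoring) | Yes, once detected | Presupposes detection |
| Contact by patient or treating physician | Retention Strategies, Management after an Event | Yes | Voluntary |
| Adverse event entry | Data Collection and Management Responsibilities | Yes | No items listed |

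**Report triggers.** Event Adjudication asks for a report from the admitting hospital. Follow-up Strategies has the investigator act once a patient has been admitted. The text under call field 2 uses death or an endpoint-related admission. Against these, Follow-up Procedures elsewhere uses any clinical event, and its general-monitoring paragraph uses any potential event detected locally. An AF episode diagnosed in an outpatient clinic meets the second group but not the first.

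**Why capture could depend on arm.** Field 3 is completed in both arms but elicits different things. In the dapagliflozin arm a crossover means stopping the drug, and a side effect is a natural reason. In the control arm a crossover means starting it, and the reason would be an indication. A control patient with the same infection has no study drug to stop and so no equivalent prompt.

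**Size.** The plan gives no expected rate, capture rate or power for AF or any safety endpoint, so it has no figure to reproduce on this point. What follows is illustration on assumed rates, with n = 510 per arm from the synopsis and two-sided α = 0.05. It ignores the anticipated 5% loss.

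Observed risk = true risk × proportion captured. The chance of a nominally significant difference is

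Φ{[|p₁ − p₀| − 1.96·√(2p̄(1 − p̄)/n)] / √[(p₁(1 − p₁) + p₀(1 − p₀))/n]}, where p̄ = (p₁ + p₀)/2.

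Worked case: true risk 5% in both arms, capture 70% against 50%. Then p₁ = 0.05 × 0.70 = 0.035 and p₀ = 0.05 × 0.50 = 0.025. Both standard errors are about 0.01068, so (0.010 − 1.96 × 0.01068)/0.01068 = −1.02, and Φ(−1.02) ≈ 0.15.

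Equal true risk, unequal capture (dapagliflozin / control):

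| Capture | Apparent ratio | Chance of a false signal, true risk 5% | Chance of a false signal, true risk 10% |
|---|---|---|---|
| 70% / 50% | 1.4 | 15% | 27% |
| 60% / 40% | 1.5 | 17% | 31% |
| 80% / 40% | 2.0 | 46% | 77% |

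With equal capture the chance stays at the nominal 5%. The apparent ratio here is just the ratio of the two assumed capture proportions, so it is an input and not a finding.

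True doubling of risk, equal capture in both arms (power):

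| Capture | 3% to 6% | 5% to 10% |
|---|---|---|
| 100% | 64% | 86% |
| 75% | 51% | 74% |
| 50% | 36% | 56% |
| 25% | 20% | 31% |

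**The case against.** The call list is not the whole of data capture. A reader might infer that reports are requested only after death or admission. The documents contradict this: Follow-up Procedures also has the history requested after any clinical event, and investigators are to report any potential event they detect. A reader might also infer that outpatient events are missed, or that new AF is under-counted. That too goes further than the text, because record review at both contacts is meant to find endpoint events and any adverse effect, adverse events are entered in the data system, and field 2 asks about emergency visits. Nor can one conclude that the follow-up eCRF lacks these items: only the baseline variables are tabulated, and the follow-up pages are not reproduced. AF needs ECG confirmation in any case, so records and not a patient's answer are the confirming source. Finally, equal under-capture need not bias a hazard ratio, and no passage shows that capture is unequal.

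All of that stands, and it limits the point to a risk. What it does not answer is that the broader triggers take effect only after someone has detected the event, that no section says which records are searched or for what, and that the one stated set of questions prompts for side effects in one arm only.

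**Conclusion.** The point holds as a gap between stated intent and stated instrument. The call fields do not carry through the AF and safety assessments that the visit diagram and schedule promise, the report triggers are inconsistent, and no structured, arm-neutral way of asking is given. Under-capture, and readier capture on dapagliflozin, are plausible in an open-label trial with no required follow-up ECG or laboratory test, but neither is demonstrated.

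The size is unknown. The illustrations show only that capture gaps of 20 to 40 percentage points, if they occurred, could matter for events with a 5% to 10% risk.

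The effect falls on a secondary endpoint and on tertiary safety endpoints. The primary composite is largely covered by fields 1 and 2. This is an inexpensive improvement that should be made; it does not threaten the main result.

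**What to change.** - Add to the 3- and 12-month call form a yes/no item with date for AF and for each of the six safety endpoints, worded identically in both arms and asked whatever the adherence answer.
- Request source records for any positive answer, including outpatient records, and for AF the ECG or rhythm strip that the definition requires.
- Reconcile the report triggers in Event Adjudication, Follow-up Strategies and Follow-up Procedures to one rule: any potential endpoint or safety event, whether or not it led to admission.

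The cost is a change to the call form and eCRF, slightly longer calls and more record requests. No test or visit is added, so the pragmatic design is kept.
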